10.1.1.1. Solicited Adverse Reactions within 7 Days of Trial Vaccine Administration

The occurrence of solicited ARs will be collected in the pre-defined diary by the subjects for 7 consecutive days following administration of vaccine dose (including the day of administration) and will be recorded on the CRF.

In this trial, solicited local ARs including pain, tenderness, erythema, and swelling. Solicited systemic ARs including headache, chills, fatigue, myalgia, arthralgia, vomiting, diarrhea, and fever occurring from the day of vaccination to 7 days post-vaccination. Solicited local and systemic ARs will be assessed as 'None', 'Mild', 'Moderate', 'Severe' or 'Potentially Life-threatening' according to defined severity grading scales as provided in protocol Table 7 and 8. Any solicited AR reported incorrectly as an unsolicited AE, as determined by the Icosavax medical lead, will be included in the solicited AR summaries, figures, and listings.

Solicited local and systemic ARs will summarized as below by vaccine group, aggregate IVX-A12, and overall:

- The number and percentage of subjects who experienced solicited ARs on each day within 7 days after the vaccine administration. The summary will be by day and overall within 7 days.
- The number and percentage of subjects who experienced solicited ARs by maximum severity.
- The number and percentage of subjects who experienced solicited ARs by number of days of occurrence (1-2 days, 3-5 days, 6+ days) and their corresponding 95% CIs.
 - Ongoing solicited ARs that become unsolicited adverse events will be included.

The above summaries will be repeated by age subgroup analyses category.

Stacked bar chart of solicited local and systemic ARs by maximum severity, and by maximum severity and age subgroup analyses category will also be provided.

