The dosage level and formulations of IVX-A12 for this Phase 2a clinical trial were selected based on the totality of the IVX-A12 nonclinical data and the interim safety and immunogenicity clinical data from the ongoing IVX-A12 Phase 1 clinical trial. Two different IVX-A12 formulations, IVX-A12a and IVX-A12d, or placebo were administered as a single IM dose to older adult subjects enrolled into two age strata (adults 60 to 69 years of age and elderly adults 70 to 85 years of age). Eligible older adult subjects were randomized to different trial groups to ensure balance among the groups. This Phase 2a clinical trial included a sentinel group of 40 subjects (16 subjects per active treatment group [n=32]; 8 subjects in the placebo group) to conservatively assess the 150 µg RSV/150 µg hMPV dosage level in combination with MF59.

Based on the interim analysis (IA) of Day 28 data from this ongoing trial and data from the Phase 1 (ICVX-12-101) trial, the sponsor has determined the trial subjects will be unblinded at Day 365. IVX-A12a and placebo recipients will be asked to be followed for an additional 12 months for safety and to return to the clinic on visit Day 730 for one immunogenicity blood draw (observational extension).

The Day 28 IA data from this Phase 2 trial demonstrated the following:

- Slightly more reactogenicity was observed in subjects who received IVX-A12 with MF59 compared to those who received IVX-A12 without MF59;

- The inclusion of MF59 did not improve the immunogenicity of 150 µg RSV / 150 µg hMPV in this older, Phase 2 population relative to the Phase 1 population; and
- The overall safety data (i.e., unsolicited adverse events [AEs], and adverse reactions [ARs]) between Phase 1 and Phase 2 were similar even with the doubling of the IVX-A12 RSV dosage level in the Phase 2 trial compared to dosage levels evaluated in the Phase 1.

IVX-A12a induced neutralizing and binding antibody responses to RSV and hMPV, which supports the selection of the unadjuvanted dosage level of 150 µg RSV/150 µg hMPV for further clinical evaluation.

The trial will be conducted in accordance with the protocol, ICH of Technical Requirements for Pharmaceuticals for Human Use, GCP Guidelines, Declaration of Helsinki, and applicable regulatory requirements.

Objectives and Endpoints:

Main Trial	
Primary Safety	
Objective	Endpoints

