3.1. Main Trial Objectives

3.1.1. Primary Safety Objective

The primary safety objective is to assess the safety and tolerability of IVX-A12 bivalent candidate vaccine with or without MF59 adjuvant compared to placebo up to 1 year following a single IVX-A12 vaccination when administered as a single-dose regimen in healthy older adults 60 to 85 years of age.

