10.1.1. Adverse Events

Adverse events are collected as solicited, unsolicited AEs, SAEs, CESIs, and MAAEs. Solicited ARs are recorded in the subject diary; unsolicited AEs are collected on AE page of case report forms (CRFs). Furthermore, a solicited ARs that is ongoing after the diary period, leads to trial discontinuation, or results in an MAAE or SAE, should be entered on the AE page of the CRF as an unsolicited AE. The following are primary endpoints: Solicited local reactions and systemic ARs from the day of dosing (Day 0) through Day 6 (Study Day 1 to Study Day 7); Unsolicited AEs from day of dosing (Day 0) through 28 days post-vaccination (Study Day 1 to Study Day 29). SAEs, MAAEs and AEs leading to trial withdrawal from day of dosing (Day 0; Study Day 1) up to the end of the main trial, CESIs (mild, moderate or severe lower respiratory tract infection (LRTI) caused by RSV and/or hMPV) from day of dosing (Day 0; Study Day 1) up to the end of the main trial, and AESIs (including anaphylaxis, thrombocytopenia, and pIMCs, including Guillain Barre's syndrome, as defined in [section 16](#)) are secondary safety endpoints. AE summaries will be performed on the Safety Set, unless otherwise stated.

An overall summary of the number and percentage of subjects reporting any solicited ARs, Grade 3 solicited ARs, Grade 4 solicited ARs, \geq Grade 3 solicited ARs any unsolicited AEs, trial vaccine-related unsolicited AEs, Grade 3 unsolicited AEs, Grade 3 trial vaccine-related AEs, Grade 4 unsolicited AEs, Grade 4 trial vaccine-related AEs, \geq Grade 3 unsolicited AEs, \geq Grade 3 unsolicited AEs, SAEs, trial vaccine-related SAEs, CESIs, trial vaccine-related CESIs, AESIs (including pIMCs), trial vaccine-related AESIs (including pIMCs), MAAEs, trial-vaccine related MAAEs, AEs leading to trial discontinuation and AEs leading to death will be provided. The summary will be repeated by vaccine group and age subgroup analyses category.

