A figure will be produced for unsolicited adverse events with a \geq 2% total frequency by vaccine group. The percentage of subjects for each vaccine group will be displayed. Also, the risk difference (the difference in percentage of subjects that experience an unsolicited AE) and corresponding 95% CI will be displayed for IVX-A12a versus Placebo and IVX-A12d versus Placebo within figure.

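### Incidence and severity of solicited reactions, a co-primary safety endpoint, are planned without any between-group difference or interval, although the objective compares with placebo

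*SAP*

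**What the plan says.** **Endpoint and objective.** SAP 10.1.1 states: "The following are primary endpoints: Solicited local reactions and systemic ARs from the day of dosing (Day 0) through Day 6". SAP 5.1.1.1 lists the same endpoint as co-primary. The objective in SAP 3.1.1 is "to assess the safety and tolerability of IVX-A12 bivalent candidate vaccine with or without MF59 adjuvant compared to placebo up to 1 year".

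**Planned summaries.** SAP 10.1.1.1 has three, each by vaccine group, aggregate IVX-A12 and overall:
- by day and over the week: "The number and percentage of subjects who experienced solicited ARs on each day within 7 days after the vaccine administration";
- by severity: "The number and percentage of subjects who experienced solicited ARs by maximum severity";
- by duration: "by number of days of occurrence (1-2 days, 3-5 days, 6+ days) and their corresponding 95% CIs".

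The first two have no interval. The third has an interval for each group. Stacked bar charts and repeats by age subgroup follow. The overall adverse event summary in SAP 10.1.1 is also counts and percentages. Protocol 13.1.5 asks for solicited reactions by day, overall and by maximum severity, and names no contrast.

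**Treatment of other endpoints.** For unsolicited events with at least 2% total frequency, SAP 10.1.1.2 plans a figure in which the risk difference and "corresponding 95% CI will be displayed for IVX-A12a versus Placebo and IVX-A12d versus Placebo within figure". For seroresponse, SAP 9.1.1.2 plans the 95% CI of the difference by Wilson's score method, for adjuvanted against unadjuvanted and for each active arm against placebo.

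**Role of reactogenicity.** Protocol 2.0 lists among the Day 28 interim findings: "Slightly more reactogenicity was observed in subjects who received IVX-A12 with MF59 compared to those who received IVX-A12 without MF59". Protocol 4.4 repeats this in explaining why the unadjuvanted formulation goes forward.

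**The concern.** A comparative objective calls for a comparative estimate. For solicited reactions the plan gives a percentage per arm and leaves the comparison, and its precision, to the reader.

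The trial's descriptive status does not explain this. SAP 7.1 says that no formal hypotheses are tested, yet the same SAP estimates differences with intervals for seroresponse and for common unsolicited events. The general line in SAP 7.1 about presenting CIs and p-values names no endpoint and no contrast, so it does not fill the gap.

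The asymmetry also matters for how the formulation decision is documented. That decision weighs immune response against reactogenicity. Seroresponse has an adjuvanted-versus-unadjuvanted difference with a CI. Neither the solicited-reaction tables nor the unsolicited event figure contains that contrast.

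**Working it through.** **1. The plan's own safety figure.** SAP 4.3.1 gives the chance of seeing at least one event among 100 subjects.
- 1 - 0.99^100 = 0.634 at 1% incidence.
- 1 - 0.98^100 = 0.867 at 2% incidence.

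Both match the stated 63.4% and 86.7%. They describe detection within one arm and say nothing about the precision of a comparison.

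**2. Inputs.** Arm sizes of 100, 100 and 50 come from SAP 4.1.1. The confidence level of 95% is the SAP's. Reaction rates are not in the documents, so all rates below are assumptions and are shown over a range.

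**3. Approximate half-width at a common rate p.** The formula is 1.96 × sqrt[p(1-p)(1/n1 + 1/n2)].
- 100 v 100: p = 10% gives 1.96 × sqrt(0.09 × 0.02) = 8.3 points; p = 50% gives 1.96 × sqrt(0.25 × 0.02) = 13.9 points.
- 100 v 50: p = 10% gives 1.96 × sqrt(0.09 × 0.03) = 10.2 points; p = 50% gives 1.96 × sqrt(0.25 × 0.03) = 17.0 points.

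**4. Score-based interval.** I take the method named in SAP 9.1.1.2 to be the Newcombe interval built from Wilson limits (l, u) for each arm:
- lower = d - sqrt[(p1 - l1)² + (u2 - p2)²]
- upper = d + sqrt[(u1 - p1)² + (p2 - l2)²]

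Worked case, 50/100 v 40/100: the Wilson limits are 40.4% to 59.6% and 30.9% to 49.8%.
- Lower = 10 - sqrt(9.6² + 9.8²) = -3.7.
- Upper = 10 + sqrt(9.6² + 9.1²) = 23.2.

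| Assumed rates | Arm sizes | Difference (95% CI), points |
|---|---|---|
| 30% v 20% | 100 v 100 | 10.0 (-2.0 to 21.7) |
| 40% v 30% | 100 v 100 | 10.0 (-3.2 to 22.7) |
| 50% v 40% | 100 v 100 | 10.0 (-3.7 to 23.2) |
| 60% v 50% | 100 v 100 | 10.0 (-3.7 to 23.2) |
| 50% v 30% | 100 v 100 | 20.0 (6.4 to 32.6) |
| 30% v 20% | 100 v 50 | 10.0 (-5.4 to 23.0) |
| 40% v 20% | 100 v 50 | 20.0 (4.1 to 33.1) |

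**5. Reading.** In the cases tried, a 10-point excess at 100 per arm has an interval about 24 to 27 points wide that includes zero, and a 20-point excess has one that excludes it. The added interval would therefore tell the reader something that the two percentages do not show directly.

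**The case against.** The strongest reply is that the trial is declared descriptive, that SAP 10.1.1.1 delivers what Protocol 13.1.5 asks for, and that no information is lost. Counts are tabulated by group with group sizes in the column headings (SAP 13.2.4), so anyone can compute a difference. Much of this stands: there is no conflict between protocol and SAP, and no test is missing. It does not explain why seroresponse and common unsolicited events get an interval for the difference and solicited reactions do not.

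Four stronger readings are tempting, and the documents do not support them.

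- *Solicited reactions have no intervals at all.* The duration categories have within-group 95% CIs.
- *The primary safety objective gets no comparative result.* Its other co-primary endpoint, unsolicited events, has a risk difference against placebo for each active arm, though only for events reaching 2%.
- *The safety objective requires a comparison of IVX-A12d with IVX-A12a.* It compares with placebo. The MF59 contrast comes from the formulation decision.
- *The gap could change the choice of formulation.* Protocol 4.4 shows that the choice was made from the Day 28 interim together with Phase 1 data, and it also rested on MF59 not improving immunogenicity. The SAP refers to October 2024, after that choice, so a contrast added now would be specified with its direction already known.

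Two limits remain. Table shells (SAP 15) and the interim output list (SAP 4.4) are separate documents that I have not seen and may hold more. Protocol 4.4 describes Day 28 reactions as mainly mild with few moderate, so Grade 3 rows may be nearly empty.

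**Conclusion.** The point holds as a reporting gap. Incidence and maximum severity of solicited reactions are planned as number and percentage only, and no solicited-reaction summary carries a between-group difference with a CI. The placebo contrasts follow directly from the stated objective. The IVX-A12d versus IVX-A12a contrast is descriptive support for a choice already made.

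The size depends on assumed rates. Half-widths are about 8 to 14 points for 100 v 100 and 10 to 17 points for 100 v 50 at common rates of 10% to 50%. On that basis an observed 10-point excess with MF59 would be compatible with no difference. This does not show that the reported Day 28 excess was due to chance, because its underlying counts are not in the documents. The change is worth making because it is cheap, needs no new data, and lets the trial estimate its own comparative objective.

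**What to change.** In SAP 10.1.1.1, keep the percentage displays that Protocol 13.1.5 requires and add the risk difference with a 95% CI, without p-values:
- **Outcomes:** any, and Grade 2 or higher, separately for local and systemic solicited reactions; Grade 3 or higher if events occur.
- **Contrasts:** IVX-A12a versus placebo, IVX-A12d versus placebo, and IVX-A12d versus IVX-A12a.
- **Method:** the Wilson-score method already in SAP 9.1.1.2. An age-stratified interval is optional.
- **Label:** mark the IVX-A12d versus IVX-A12a contrast as descriptive support for the formulation chosen after the Day 28 interim.

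Add IVX-A12d versus IVX-A12a to the unsolicited event figure in SAP 10.1.1.2.

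The cost is SAP wording, a few table columns and one more contrast in a figure. The downside is more unadjusted intervals: 2 reaction types × 2 thresholds × 3 contrasts = 12 in the main tables, or 18 with Grade 3 or higher. The text should say that they are not adjusted for multiplicity.

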10.1.1.2. Unsolicited Adverse Events

An unsolicited AE is an AE that was not solicited using the post-vaccination diary and that was spontaneously communicated by a subject. Unsolicited AEs will be collected for 28 days following the administration of the vaccination. Any solicited AR observed as continuing Day 7 following trial vaccination will be additionally recorded as an unsolicited AE.

Unsolicited AEs will be classified by system organ class (SOC) and preferred term (PT) according to MedDRA version 26.0 or greater.

The severity of AEs is determined by the investigator as Mild (Grade 1), Moderate (Grade 2), Severe (Grade 3), and Potentially Life-threatening (Grade 4). If there are events with missing severity, the category 'Missing' will be summarized separately from the non-missing categories.

The relationship (causality) of AE to the vaccine will be assessed by the investigator as Related and Not Related. If there are events with missing relationship, the category 'Missing' will be summarized separately from the non-missing categories.

Any solicited AR reported incorrectly as an unsolicited AE, as determined by the Icosavax medical lead, will be included in the unsolicited adverse event summaries and listings.

Unsolicited AEs will be summarized as below by vaccine group, aggregate IVX-A12, and overall:

This document is confidential.

- The number and percentage of subjects reporting unsolicited AEs by SOC and PT.
- The number and percentage of subjects reporting unsolicited AEs by SOC, PT and maximum severity.
- The number and percentage of subjects reporting \geq Grade 3 unsolicited AEs by SOC and PT.
- The number and percentage of subjects reporting vaccine-related unsolicited AEs by SOC and PT.
- The number and percentage of subjects reporting \geq Grade 3 and vaccine-related unsolicited AEs by SOC and PT.

All above summaries will be repeated by age subgroup analyses category.

Summaries will be ordered by descending frequency of SOC, and then within each SOC, by overall descending frequency of PT in the total column. If a subject has one or more unsolicited AEs more than once, the subject is counted only once under any given SOC or PT.

A figure will be produced for unsolicited adverse events with a \geq 2% total frequency by vaccine group. The percentage of subjects for each vaccine group will be displayed. Also, the risk difference (the difference in percentage of subjects that experience an unsolicited AE) and corresponding 95% CI will be displayed for IVX-A12a versus Placebo and IVX-A12d versus Placebo within figure.

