2.2. Timings of Analyses

An independent safety monitoring committee (SMC) will be constituted to monitor the safety of all subjects enrolled in the trial, including solicited local adverse reactions (ARs), solicited systemic ARs, unsolicited adverse events (AEs), and clinical laboratory data. The SMC will review safety data collected during the 7 consecutive days following vaccination for all subjects, focusing on the interpretation of solicited local ARs and solicited systemic ARs, unsolicited AEs and clinical laboratory data in the first week after dosing when most reactogenicity is expected to occur. Details of the membership, roles and functioning of the committee will be available in the SMC charter.

Further description of the SMC analyses can be found in the SMC charter. The SMC charter was authored by Icosavax Inc. For the closed SMC session, an unblinded team from Syneos Health Biostatistics will perform the analyses as described in [Section 4.4](#) of this SAP to maintain the blinding of the trial.

Two interim analyses (IA) will be performed: the first when all subjects have completed the Day-28 safety assessments and all Day-28 immunogenicity data are available; the second when all subjects have completed the Day-180 safety assessments and all Day-180 secondary immunogenicity data are available. These analyses will support further evaluation of safety and immunogenicity of IVX-A12 in older adults. The purpose of the interim analyses will be used for confirmation of dosage level and formulation selected for further evaluation in older adults 60 years of age or older. For each of the interim analyses, a data-cut will be performed. For the Day-28 interim analysis, all data through day 28 will be included. For the Day-180 interim analysis, all data through day 180 will be included. Additional details regarding the data cut will be found in the *Data Cut-Off Guidance* document.

A primary analysis is planned after all subjects complete the final trial visit, Day 365, or terminate early from the trial and all data is available. The open label extension of the trial starting after Visit Day 365 was discontinued early, prior to the subjects completing Day 545. The limited amount of data from the extension will be reported once all data are available.

This document is confidential.

3. Study Objectives

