4.3. Determination of Sample Size

4.3.1. Main Trial Determination of Sample Size

Sample size for this trial is not based on any formal hypothesis testing. Analyses of safety and immunogenicity will be primarily descriptive in nature. An approximate total of 250 subjects (approximately 100 subjects in each of the IVX-A12 groups and 50 subjects in the placebo group) will be randomized. With 100 subjects in each IVX-A12, there is a 63.4% probability of observing at least 1 subject with an AE if the true incidence of the AE is 1% and 86.7% probability of observing at least 1 subject with an AE if the true incidence of the AE is 2%. The trial will have more than 90% power to detect a difference of 20% or more in seroresponse rate (SRR) or detect a 2-fold increase or more in GMT or GMFR (assuming standard deviation at $0.5 \log_{10}$), between the two IVX-A12 groups (or between the IVX-A12 group and placebo group), with a two-sided type-1 error rate at 0.05.

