5.1. Main Trial Endpoints

5.1.1. Primary Endpoint(s)

5.1.1.1. Co-primary Endpoints (Safety)

- Solicited local (injection site) reactions and systemic ARs for 7 consecutive days starting from Day 0 to Day 6;
- Unsolicited AEs from Day 0 to Day 28.

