Using an ANCOVA, the adjusted GMTs and GMFRs at Day 28 and its 95% CI will be calculated. The outcome variable is Day 28 log2 transformed titers. The factors will include vaccine group, age stratification category, and gender and the covariates will include, log2 transformed baseline titers. Least square means and 95% CIs are back transformed to provide geometric means. To assess whether an adjuvant is required in the formulation to enhance immune responses to IVX-A12, pairwise comparison of the GMT and GMFR least square means from this modeling between non-adjuvant and adjuvant groups will also be displayed. Also, to assess an improvement between the active treatments (IVX-A12a and IVX-A12d) versus placebo, pairwise comparison of the GMT and GMFR least square means from this modeling between IVX-A12a and Placebo and IVX-A12d and Placebo will be displayed. No adjustments for multiplicity will be performed. Data displays will also include boxplots of titers for anti-RSV/A-, RSV/B-, hMPV/A-, and hMPV/B specific NAb ([live-virus assays]) and RSV and hMPV IgG prefusion F protein-specific antibody titers ([ELISAs] at Day 28 for all ages. Log2 transformed titers will be used to create boxplots and back-transformed. The y-axis will be on a log scale. For anti-RSV/A- and RSV/B, the y-axis will display both sets of units.

The above analysis will be repeated as follows:

- By age subgroup analyses category. When using an ANCOVA, the outcome variable is Day 28 log2 transformed titers. The factors will include vaccine group, age stratification category and gender and the covariate is log2 transformed baseline titers;

This document is confidential.

- By baseline tertile; When using an ANOVA, the outcome variable is Day 28 log2 transformed titers. The factors will include vaccine group, age stratification category and gender;
- By age subgroup analyses category and baseline tertile. When using the ANOVA, the factors will include vaccine group, age stratification category, and gender.

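### The SAP plans no IVX-A12d minus IVX-A12a risk difference with a confidence interval for unsolicited AEs, although the two arms differ only in MF59

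*SAP*

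**What the plan says.** SAP 5.1.1.1 lists "Unsolicited AEs from Day 0 to Day 28" among the co-primary safety endpoints. SAP 10.1.1.2 tabulates these events by vaccine group, aggregate IVX-A12 and overall. It then adds a graphical output: "A figure will be produced for unsolicited adverse events" that reach 2% total frequency. Two things go into that figure. First, "The percentage of subjects for each vaccine group will be displayed". Second, risk differences with 95% CIs, which "will be displayed for IVX-A12a versus Placebo and IVX-A12d versus Placebo within figure". The CI method is not named, and nothing else in SAP 10.1 contrasts one formulation with the other.

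The immunogenicity sections go further. SAP 9.1.1.1 states a purpose and a contrast: "To assess whether an adjuvant is required in the formulation to enhance immune responses to IVX-A12, pairwise comparison of the GMT and GMFR". It compares the adjuvanted and unadjuvanted arms on model-adjusted means, and sets each formulation against placebo as well. SAP 9.1.1.2 plans the same three contrasts for the seroresponse rate, with Wilson-score intervals.

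On use of the data, Protocol 4.4 says that safety as well as immunogenicity results will inform the choice of formulation. SAP 2.2 says of both interims that they "will be used for confirmation of dosage level and formulation selected for further evaluation in older adults 60 years of age or older". SAP 3.1.1 words the primary safety objective as the vaccine, with or without MF59, against placebo.

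**The concern.** Protocol Table 2 gives both active arms 150 µg RSV and 150 µg hMPV. The only listed difference is MF59: 0 v 9.75 mg squalene. The randomised comparison that isolates the adjuvant is therefore IVX-A12d against IVX-A12a. The immune side of that question receives a direct estimate with an interval. The unsolicited-AE side receives two intervals that share one comparator of 50 subjects.

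Anyone who wants to say what MF59 adds to unsolicited AEs must either subtract two percentages and report no uncertainty, or look at whether one placebo interval excludes zero and the other does not. The second habit is a familiar source of spurious formulation differences. At stake is how well the final report can support a statement on the unsolicited-AE effect of MF59.

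**Working it through.** **Inputs from the documents.** Arm sizes are "approximately 100 subjects in each of the IVX-A12 groups and 50 subjects in the placebo group" (SAP 4.3.1), and intervals are 95%. The documents give no expected unsolicited-AE rates, so every rate below is an assumption.

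**The plan's own AE figures.** The chance of at least one event among 100 subjects is 1 − (1 − p)^100. At p = 1% this is 63.4%; at p = 2% it is 86.7%. Both stated values reproduce. With the 50 placebo subjects the same formula gives 39.5% and 63.6%.

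**Precision at a common rate p.** The half-width of a risk-difference CI is about 1.96 × √[p(1 − p)(1/n₁ + 1/n₂)].

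- IVX-A12d v IVX-A12a: 1/100 + 1/100 = 0.02.
- Either formulation v placebo: 1/100 + 1/50 = 0.03.
- Width ratio: √(0.02/0.03) = 0.816, so the direct interval is about 18% narrower.

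| Assumed rate | A12d v A12a | Formulation v placebo |
|---|---|---|
| 2% | ±3.9 points | ±4.8 points |
| 5% | ±6.0 | ±7.4 |
| 10% | ±8.3 | ±10.2 |
| 20% | ±11.1 | ±13.6 |
| 30% | ±12.7 | ±15.6 |

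**What can be recovered from the planned display.** The point difference can: (d − placebo) − (a − placebo) = d − a. The interval cannot be built from the two placebo intervals as if they were independent, because the placebo arm would be counted twice. That route gives 0.03 + 0.03 = 0.06 in place of 0.02, a half-width of 14.4 points at a 10% rate. This is √3 ≈ 1.7 times the direct 8.3.

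An illustration with assumed counts 30/100 (A12d), 20/100 (A12a) and 8/50 (placebo), Newcombe intervals:

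- A12d − placebo: 14 points (−0.9 to 26.3) – planned.
- A12a − placebo: 4 points (−10.2 to 15.7) – planned.
- A12d − A12a: 10 points (−2.0 to 21.7) – not planned.

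**Where the precision gain shrinks.** I simulated 200,000 trials per scenario with Newcombe intervals, both formulations equal and 10 points above placebo.

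| A12d / A12a / placebo | Direct interval narrower by |
|---|---|
| 15% / 15% / 5% | about 1% |
| 20% / 20% / 10% | about 6% |
| 30% / 30% / 20% | about 11% |

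The gain nearly vanishes in the first row because the placebo arm, though small, has a much lower binomial variance: 0.05 × 0.95 = 0.0475 against 0.15 × 0.85 = 0.1275.

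**Disagreement between the two placebo intervals.** In those same three scenarios one placebo interval excludes zero and the other does not in about 22% to 27% of trials, although the formulations are identical. The direct interval wrongly excludes zero in about 5%. When all three arms are equal the contrast is small: 5.2% disagreement v 3.6% direct error at a 5% rate, and 5.8% v 4.4% at a 10% rate.

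**The case against.** Several points on the other side stand.

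- **The data are shown.** A reader might infer that the adjuvant comparison has no safety estimate on this endpoint. That is too strong. SAP 10.1.1.2 gives percentages per vaccine group in the figure and in every SOC/PT, severity and relatedness table, and SAP 10.1.1 gives overall rows. Only the between-formulation difference with its CI is missing, and a CI can be computed from the printed counts.
- **The plan does not contradict itself.** The placebo contrasts match the primary safety objective in SAP 3.1.1. The adjuvant question is written explicitly only into the immunogenicity analysis.
- **The sizing does not promise an AE contrast.** SAP 4.3.1 mentions the active-v-active comparison for SRR, GMT and GMFR. Its AE statement concerns only the chance of seeing at least one event.
- **No decision rule is prescribed.** SAP 7.1 states that no formal hypotheses are tested. Comparing which placebo interval excludes zero is a reading that the display invites, not one that the SAP prescribes, so the disagreement rates measure a risk of misreading.
- **Resolution stays limited.** Under assumed rates of 10% v 5%, the direct interval would exclude zero in about 24% of trials; at 5% v 2%, about 16%. It will rarely settle a modest effect on a single term.
- **The choice was already made.** Protocol 4.4 records IVX-A12a as selected, and the MF59 safety difference it cites is reactogenicity, a solicited outcome. A reader might infer that the missing contrast undermines that selection; the documents do not support this.
- **Some outputs could not be checked.** The interim output list and the table shells are separate documents.

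What does not stand is the argument that a descriptive trial needs no such contrast. The immunogenicity analyses are equally descriptive and include it, and the SAP has already chosen to show AE risk differences with intervals.

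**Conclusion.** The omission is real and limited. As written, the SAP gives no interval for the effect of MF59 on unsolicited AEs, while it does so for every primary immunogenicity measure. The gap concerns the formulation question; the placebo-framed safety objective is served as planned.

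The direct interval would be about 18% narrower than the placebo intervals if AE rates are similar across arms, and as little as 1% to 11% narrower if both formulations are equal and 10 points above placebo. In the latter case its main value is protection against a false formulation difference: about 5% error against about 22% to 27% disagreement between the placebo intervals. These figures assume arms of 100, 100 and 50, Newcombe intervals for the simulated results, and AE rates that the documents do not supply.

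Because IVX-A12a had already been chosen, the benefit lies in final reporting. It is a cheap improvement, not a defect that threatens the trial's conclusions.

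**What to change.** In SAP 10.1.1.2, extend the risk-difference sentence to include IVX-A12d versus IVX-A12a, and name the interval: the Wilson-score (Newcombe) 95% CI, in line with SAP 9.1.1.2. State that any conclusion about MF59 and unsolicited AEs rests on this contrast and not on comparing the two placebo contrasts. Keep both placebo contrasts.

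Optionally, show the same three contrasts for subjects with any unsolicited AE, any vaccine-related one, and any of Grade 3 or higher.

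The core change needs one sentence and one more column or panel from data already collected. The downside is one more unadjusted descriptive interval per term; the optional rows add a small extra table.
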